9.3.3. Censoring

The censoring date will be the minimum date in follow-up (starting >14 days after vaccination) of the following variables.

Table 3. Censoring Variables

Variable	Role	Operational definition
Outcome under study	Censoring	See outcome table above. Table 2 .
Disenrollment	Censoring	Date a patient disenrolls from the insurance plan, as indicated in the enrollment file.
End of data	Censoring	14 February 2023
Receipt of second vaccine of the same type	Censoring	Any kind of mRNA bivalent COVID-19 vaccine is considered as a censoring vaccine. See exposure table for vaccination definitions.
Receipt of the other vaccine type	Censoring	Any kind of mRNA bivalent COVID-19 vaccine is considered as a censoring vaccine. See exposure table for vaccination definitions.
Death	Censoring	Death date is assigned the midpoint of the month in which death is reported in the database.
Nirmatrelvir/ritonavir (sensitivity analysis for COVID-19 endpoints)	Censoring	First dispensing for Nirmatrelvir/ritonavir during follow-up using NDC codes.
Influenza treatment (sensitivity analysis for treatment endpoints)	Censoring	First dispensing of any influenza treatments (see outcome table above for definitions) during follow-up using NDC codes.

PFIZER CONFIDENTIAL

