9. RESEARCH METHODS

9.1. Study Design

[figure not shown]
This structured secondary data collection study will be a retrospective, cohort design to describe concomitant vaccine uptake and subsequent outcomes during one influenza vaccination season. Individuals will be indexed on the date of their first Pfizer-BioNTech mRNA bivalent COVID-19 or influenza vaccine. Exposure groups will be assigned as follows:

- Group 1: Same day (Pfizer-BioNTech mRNA bivalent COVID and flu on the same day);
- Group 2: COVID alone (Pfizer-BioNTech bivalent COVID only);
- Group 3: flu alone (influenza vaccine of any type only).
- CCI

A one year lookback period prior to the index vaccination will be used to identify covariates. Individuals will be followed starting 15 days after vaccination until experiencing one of the following: 1) outcome 2) disenrollment 3) receipt of a second vaccine of the same type 4) receipt of the other vaccine or any type of COVID-19 vaccine 5) end of data or 6) death. Only Pfizer-BioNTech mRNA bivalent COVID-19 vaccine will be assessed. All types of influenza vaccines recommended for the eligible population will be eligible for inclusion, but for the 65+ age group only enhanced influenza vaccines will be included.

PFIZER CONFIDENTIAL

Figure 1. Overall Study Design

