Urinary tract infection	Negative control outcome	≥1 ICD-10-CM diagnosis code in any position/any setting for a urinary tract infection (that occurs >14 days after the patient's first mRNA bivalent COVID-19 or influenza vaccine dose during the study period).
Accidental injury	Negative control outcome	≥1 ICD-10-CM diagnosis code in any position/any setting for accidental injury that occurs >14 days after the patient's first mRNA bivalent COVID-19 or influenza vaccine dose during the study period.
Hospitalization in the 14 days following vaccination (recently vaccinated) Day 1-14	Negative control outcome	
An inpatient (acute facility) claim that meets the following criteria:
 
 1. Occurs ≤14 days after the patient's first mRNA bivalent COVID-19 or influenza vaccine dose during the study period.

PFIZER CONFIDENTIAL

Table 2. Outcome Variables

Variable	Role	Operational definition
		2. Place of service = 21. 3. Non-null confinement ID.
CCI		
CCI		
CCI		
CCI		

PFIZER CONFIDENTIAL

Table 2. Outcome Variables

Variable	Role	Operational definition
		within 60 days following discharge.
CCI [REDACTED]	[REDACTED]	[REDACTED]
Follow-up time	Outcome descriptive	Measured from day 15 through the minimum date of censoring (see follow-up time description in Section 9.3.3). Mean, standard deviation (SD), median (Q1-Q3), minimum, and maximum, will also be summarized for the length of follow-up in each group.

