9.4. Data Sources

Optum's Clininformatics Data Mart (CDM) comes from a database of administrative health claims for members of a large national managed care company affiliated with Optum. The database includes over 73 million unique lives (2007 through 2021). Clininformatics Data Mart is statistically de-identified under the Expert Determination method consistent with HIPAA and managed according to Optum customer data use agreements. These administrative claims submitted for payment by providers and pharmacies are verified, adjudicated, adjusted, and de-identified prior to inclusion. The Claims data comprises both commercial/employer sponsored plans and Medicare Advantage health plan data. This data covers ~30% of the national Medicare Advantage population. The population is geographically diverse, spanning all 50 states. In addition to medical claims and pharmacy claims, the Claims data includes tables with member eligibility and inpatient confinements. The Claims data also includes standard pricing for all medical claims, pharmacy claims, and inpatient confinements. Mortality is provided as month and year of death and is sourced from Centers for Medicare and Medicaid Services, Social Security Administration Death Master File, facility claims with inpatient death, discontinuation of coverage due to death and external obituary data.

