Each outcome will be assessed separately. Experiencing one disease specific outcome is not a censoring criteria for the other disease (ie, having a COVID-19 outpatient diagnosis is not a censoring event for the influenza endpoints). Weighted cumulative incidence curves will be used to describe the occurrence of each outcome separately over the entire follow-up period. Given the relatively short follow-up time, we expect small numbers of deaths. Therefore, regular Cox proportional hazards models will be used to estimate HRs and 95% CI for each outcome separately. If we find that death is more common than anticipated, we will consider using Fine and Gray's proportional subdistribution hazards models to account for the competing risk of death. Models for the following vaccine group/outcome combinations will be assessed:

- Same day/COVID-19 only:
 - All-cause hospitalization, composite COVID-19 hospitalization/ED/UC (any position), COVID-19 hospitalization (any position, primary position), COVID-19 ED/UC, COVID-19 outpatient
- Same day/Flu only:
 - All-cause hospitalization, composite flu-hospitalization/ED/UC (any position), flu-hospitalization (any position, primary position), flu ED/UC, flu outpatient.

CCI

Sensitivity Analysis

For disease specific endpoints, we will conduct a sensitivity analysis whereby an additional censoring criteria will be applied. For COVID-19 specific endpoints, we will censor for Paxlovid dispensing. For influenza specific endpoints, we will censor for any of the following influenza treatment dispensing (Oseltamivir phosphate, Zanamivir, Peramivir, Baloxavir marboxil).

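### Mid-month death censoring in Table 3 drops a first outcome claim dated later in the month of death; the effect is small and easily fixed

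*Combined protocol and SAP*

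**What the plan says.** Section 9.4 limits what is known about death: "Mortality is provided as month and year of death". The sources it lists include "facility claims with inpatient death, discontinuation of coverage due to death".

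Table 3 in Section 9.3.3 fills in the missing day: "Death date is assigned the midpoint of the month in which death is reported in the database". The sentence above the table says "The censoring date will be the minimum date in follow-up", and the table lists the outcome and death side by side, with disenrollment, further vaccination and end of data (14 February 2023). Table 2 defines follow-up time the same way, "Measured from day 15 through the minimum date of censoring", and Section 9.1 gives a matching stopping list: "Individuals will be followed starting 15 days after vaccination until experiencing one of the following".

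Section 9.7 uses the resulting times in two ways. Cox models give the hazard ratios, and "Weighted cumulative incidence curves will be used to describe the occurrence of each outcome separately". On mortality it says "Given the relatively short follow-up time, we expect small numbers of deaths", with Fine and Gray models as a fallback if deaths are more common.

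No visible text says what happens when a claim is dated after the assigned death date. Section 9.7 states that there is no separate SAP.

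**The concern.** Assigning a mid-month date is a reasonable response to month-level death data. The difficulty arises when that date is placed in a minimum with dates that were actually observed. A claim for care on the 20th shows that the patient was alive on the 20th, yet the rule treats the patient as dead on the 15th or 16th and drops the claim.

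The events at risk are those closely followed by death, so the loss falls mainly on the hospitalization outcomes. All-cause hospitalization is part of Primary Objective 2 and is modelled in both comparisons. Section 9.8 says that analyses are programmed to the protocol and double programmed. Two programmers following the same rule would both drop the event, so the quality check would not reveal it.

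A smaller gap is related. Exclusion 1 in Section 9.2.2 removes patients who died within 14 days of the first dose without saying which death date applies. If it is the assigned date, a patient vaccinated on 10 October who died on 30 October is assigned 15 or 16 October and excluded.

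**Working it through.** **1. The rule applied to example dates** (indexed early enough to be in follow-up, no other censoring)

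| First outcome claim | True death | Assigned death | Result |
|---|---|---|---|
| 20 Dec 2022 | 27 Dec | 15 or 16 Dec | claim dropped |
| 18 Jan 2023 | 30 Jan | 15 or 16 Jan | claim dropped |
| 10 Dec 2022 | 27 Dec | 15 or 16 Dec | counted |
| 20 Nov 2022 | 3 Dec | 15 or 16 Dec | counted |
| 10 Feb 2023 | 25 Feb | about 14 Feb | counted |

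A loss therefore needs a first outcome after mid-month in the same calendar month as the death. This can happen for deaths from September to January. February is unaffected because data end on 14 February, which is itself the midpoint.

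**2. Share of fatal first stays lost.** The documents give no admission-to-death interval, so it is varied. Assumption: death is equally likely on each of the 123 days from 1 October 2022 to 31 January 2023. A stay is lost if (day of death − interval) is later than the assigned day. The two columns reflect the two readings of the midpoint.

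| Interval, days | Midpoint day 15 | Midpoint day 16 |
|---|---|---|
| 0 | 63/123 = 51.2% | 59/123 = 48.0% |
| 3 | 51/123 = 41.5% | 47/123 = 38.2% |
| 7 | 35/123 = 28.5% | 31/123 = 25.2% |
| 10 | 23/123 = 18.7% | 19/123 = 15.4% |
| 14 | 7/123 = 5.7% | 3/123 = 2.4% |
| 16 | 0% | 0% |

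If intervals are spread geometrically with a mean of 5 to 14 days, the share lost is 19-36%.

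**3. Share of all hospitalization events lost** = fatality × share lost. Fatality of 2-5% is an assumption.
- 0 days: 2% × 48.0-51.2% = 1.0%; 5% × 48.0-51.2% = 2.4-2.6%.
- 3 days: 0.8% and 1.9-2.1%.
- 10 days: 0.3-0.4% and 0.8-0.9%.
- 16 days: 0%.

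These figures halve if only half of fatal stays are the patient's first event. They are smaller for composites that include ED and urgent care visits.

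**4. Power, 65+ COVID-19 composite, Group 1 vs Group 2** (Section 9.5: margin 1.15, one-sided alpha 0.025, 63% in Group 1, 0.56% with an event).
- The plan's own figure: (1.960 + 0.842)² / (0.63 × 0.37 × (ln 1.15)²) = 1,724 events, as stated.
- Events expected from Table 5: 0.0056 × (382,806 + 225,842) = 3,408.
- Power = Φ(√(3,408 × 0.63 × 0.37) × ln 1.15 − 1.960) = Φ(3.939 − 1.960) = 97.6%.
- With 2% lost, 3,340 events: Φ(3.900 − 1.960) = 97.4%.

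**5. Hazard ratio.** Equal proportional loss in both groups leaves it essentially unchanged. A hypothetical loss of 0% in one group and 2% in the other multiplies it by 0.98/1.00 = 0.98 or 1.00/0.98 = 1.02, against a margin of 1.15.

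**The case against.** The strongest reply is that this hardly matters. Some imputation is unavoidable, the protocol states its rule openly, the same rule applies to every group, few deaths are expected, and power barely moves. All of that stands and keeps the point minor. The Fine and Gray fallback is no answer, however, because it addresses death as a competing risk and not the dropping of an observed event.

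A second reply concerns the remedy. If only outcome claims may override the assigned date, late-month events enter the numerator while late-month survival of event-free decedents stays out of the denominator, and the event itself decides whether follow-up continues. This is a fair objection. It is why the fix below uses a claim for care of any kind and adds a uniform sensitivity analysis. The same reasoning rules out exempting patients from exclusion 1 because they have a later claim, since eligibility would then depend on care after vaccination.

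A reader might also infer that the claim for a fatal stay supplies the date that removes it. The documents go less far. An inpatient-death claim may be one source of the month of death, but it is Table 3 that creates the mid-month date.

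**Conclusion.** The rule is wrong as written, and the consequence is minor. Followed exactly, Table 3 discards a first outcome claim dated after mid-month in the reported month of death, and no visible text overrides it. Confidence in the mechanism is high.

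The size cannot be computed from the documents. With fatality of 2-5%, intervals of 0 to 16 days and death days uniform over October to January, about 0-2.6% of hospitalization events are lost. The certain effect is that the cumulative incidence of hospitalization is slightly too low.

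A reader might infer that the vaccine effectiveness estimates or a non-inferiority conclusion are biased. The documents do not support this: nothing in them shows a loss that differs between groups, and even a wholly one-sided 2% loss moves the hazard ratio by only about 2%. Nor is there a meaningful loss of power. The reason to act is that a stated rule drops observed events and the correction is cheap.

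**What to change.** - **Table 3:** set the assigned death date to the later of mid-month and the service date of the patient's last claim for care of any kind (not only the outcome) in the reported month of death. Disenrollment, end of data and the other censoring dates still apply. An observed outcome in that month then counts.
- **Sensitivity analysis:** add one run that censors all decedents uniformly at month-end, or at disenrollment or end of data if earlier.
- **Exclusion 1:** name the death date it uses, with no exemption based on later claims.

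The cost is one sentence in each of the two places, a small derivation change and one extra run. The downsides are limited. The primary analysis gains at most 16 days of follow-up per affected decedent (day 31 − day 15), and follow-up depends slightly on having a claim. The month-end analysis removes that dependence but adds about 15-16 days per decedent on average, some of it after the true death, so it is better kept as a sensitivity analysis.

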9.3.4. Covariates

Table 4. Covariates		
Variable	Role	Operational definition
Age	Patient Characteristics, Subgroup	
The number of years between the index date and the patient birth year. Age will be reported in the following categories: 18-64 and 65+.
 
Continuous statistics including mean, standard deviation (SD), median (Q1-Q3), minimum, and maximum, will also be summarized.
 
Model specification: continuous linear

Sex	Patient Characteristics	
Sex will be reported as Male ('M'), Female ('F'), and Unknown
 
Model specification: categorical

US Geographic Region	Patient Characteristics	
US geographic region will be derived from the patient state and categorized into the following:
 
Northeast – Connecticut, Maine, Massachusetts, New Hampshire, Rhode Island, Vermont, New Jersey, New York, Pennsylvania
 
Midwest – Indiana, Illinois, Michigan, Ohio, Wisconsin, Iowa, Kansas, Minnesota, Missouri, Nebraska, North Dakota, South Dakota
 
South – Delaware, District of Columbia, Florida, Georgia, Maryland, North Carolina, South Carolina, Virginia, West Virginia, Alabama, Kentucky, Mississippi, Tennessee, Arkansas, Louisiana, Oklahoma, Texas
 
West – Arizona, Colorado, Idaho, New Mexico, Montana, Utah, Nevada, Wyoming, Alaska, California, Hawaii, Oregon, Washington
 
Other/unknown – Puerto Rico/unknown region
 
Model specification: categorical

Charleston Comorbidity Index (CCI)	Patient Characteristics	
Charleston Comorbidity Index score will be measured during the 12 month baseline period before index and will be reported in the following categories: 0, 1, and 2+. Continuous statistics including mean, standard deviation (SD), median (Q1-Q3), minimum, and maximum, will also be summarized.
 
Model specification: categorical (0,1,2+)

Prior Pneumonia or respiratory failure	Patient Characteristics	Any code (any setting) within the 1 year baseline for any type of pneumonia or respiratory failure
Prior heart disease	Patient Characteristics	Any code (any setting) within the 1 year baseline for heart disease
Prior asthma	Patient Characteristics	Any code (any setting) within the 1 year baseline for asthma

PFIZER CONFIDENTIAL

Table 4. Covariates

Variable	Role	Operational definition
Prior chronic lung disease	Patient Characteristics	Any code (any setting) within the 1 year baseline for chronic lung disease
Prior diabetes	Patient Characteristics	Any code (any setting) within the 1 year baseline for diabetes
Prior kidney disorders	Patient Characteristics	Any code (any setting) within the 1 year baseline for kidney disorders
Month of index date	Patient Characteristics	August/September, October, November, December, January (Note: August will be combined with September as only 1 day of August will be included in the cohort). Model specification: categorical
Prior Influenza vaccination	Patient Characteristics	One claim (NDC or CPT) for influenza vaccine of any type measured between 31 August 2021 – 31 May 2022 Model specification: dichotomous (yes/no)
COVID-19 vaccination in the 1 year prior	Patient Characteristics	One claim (NCD, CPT, procedures) for COVID vaccine of any type in the 365 days before index separated into the following time periods: 
 Recent vaccination: ≤ 60 days prior to index Older vaccination: Between 61 and 365 days prior to index No evidence of vaccination in the prior year If there is evidence of >1 COVID vaccination in the 365 days prior to index, patients are categorized using the date of the most recent dose administered during the baseline period. Model specification: categorical (3 level)
Time from last COVID-19 vaccine dose (Due to the likelihood of misclassification, this variable will be used for descriptive table only, not for model)	Patient Characteristics	Number of days from last COVID-19 vaccine dose. Reported as categories: ^{17,18} <60 days, 60-179, ≥ 180 , not applicable. Continuous statistics including mean, standard deviation (SD), median (Q1-Q3), minimum, and maximum, among those with a prior dose.
Monovalent mRNA COVID-19 vaccine in the 60 days prior to index (Note for descriptive table only, not for model due to collinearity with covid vaccine in the prior year above)	Patient Characteristics	Yes/No. One claim (NCD, CPT, procedures) for monovalent mRNA COVID-19 vaccine between 01 July 2022 – 30 August 2022

PFIZER CONFIDENTIAL

Table 4. Covariates

Variable	Role	Operational definition
Type of index influenza vaccine administered (Note for descriptive table only, not for model)	Patient Characteristics	
Categories include: Enhanced/Standard/Unknown, and each specific type of vaccine
 
 • Standard 
 • Egg-based standard dose injection (Afluria, Fluarix, FluLaval, FluZone Standard Dose) • FluZone intradermal • Flucelvax (cell-based) • FluMist • Multiple • Enhanced 
 • FluZone High dose (Enhanced) • Flublok (recombinant/Enhanced) • Fluad (adjuvanted/Enhanced) • Multiple • Unknown 
See below for operational definition for assigning specific flu vaccines.

Concurrent Shingrix vaccination (any dose)	Patient Characteristics	
NDC or CPT code for Shingrix on the same day as the index vaccination
 
Model specification: dichotomous (yes/no)

Prior Shingrix vaccination	Patient Characteristics	
NDC or CPT code for Shingrix in the 365 days prior to index
 
 • 1 prior dose • 2 prior doses (measured on unique days) 
Model specification: dichotomous (yes/no) (Note: number of doses used in descriptive table only)

Concurrent pneumococcal vaccination	Patient Characteristics	
NDC or CPT code for polysaccharide or conjugate pneumonia vaccine on the same day as the index vaccination
 
Model specification: dichotomous (yes/no)

PFIZER CONFIDENTIAL

Table 4. Covariates

Variable	Role	Operational definition
Prior pneumococcal vaccination	Patient Characteristics	NDC or CPT code for polysaccharide or conjugate pneumonia vaccine in the 365 days prior to index Model specification: dichotomous (yes/no)
Vaccine administration setting	Patient Characteristics	Vaccine administration setting will be determined based on the reported place of service for the claim. Prescription claims will be assumed to have occurred in the Pharmacy setting. The most common settings will be reported and patients with multiple conflicting administration setting codes on index will be classified as multiple. Model specification: pharmacy, office, other
Nursing home residence	Patient Characteristics	Any claim with care location (POS =32) of nursing home in the 365 days prior to index. Model specification: dichotomous (yes/no)
Skilled nursing facility	Patient Characteristics	Any claim with care location of SNF (POS = 31) in the 365 days prior to index. Model specification: dichotomous (yes/no)
Functional status/mobility	Patient Characteristics	A procedure code indicating decreased functional status or mobility in the 365 days prior to index. Model specification: dichotomous (yes/no)
Wellness visit	Patient Characteristics	A CPT or diagnosis code for wellness visit in the 365 days prior to index. Model specification: dichotomous (yes/no)
Immunocompromised status	Patient Characteristics	Assess this group as the following category (Yes/No): ≥ 1 IC condition. Any code within the 1 year baseline for the following conditions: 
 • Hematologic malignancy • HIV/AIDS • Solid organ transplant • Bone marrow transplant • Primary immunodeficiencies • Immunosuppressive medications (eg, chemotherapy, oral corticosteroids ≥ 20mg of prednisone or equivalent for ≥ 14 days). Model specification: dichotomous (yes/no)
Conditions that place or may place patients at risk of Severe COVID-19	Patient Characteristics	Assess this group as the following category (Yes/No): ≥ 1 high risk condition. Baseline comorbid conditions that place or may place

PFIZER CONFIDENTIAL

Table 4. Covariates

Variable	Role	Operational definition
		
patients at risk of Severe COVID-19 will be assessed in the 12 months prior to index date. Conditions will be assessed by having at least 1 ICD-10-CM code in any position in any setting. The conditions include:
 
• Cancer history• Chronic kidney disease (CKD) at any stage• Chronic liver disease• Chronic lung diseases• Dementia or other neurological conditions• Diabetes (type 1 or type 2)• Disabilities; including Down Syndrome• Heart conditions (heart failure; coronary artery disease; or cardiomyopathies)• HIV infection• Hypertension• Immunocompromised state (primary caused by genetic defects; secondary/acquired from prolonged use of corticosteroids or other immune weakening medicines)• Mental health conditions• Overweight and obesity• Physically inactive• Sickle cell disease (SCD) or thalassemia• Smoking; current or former• Solid organ or blood stem cell transplant (includes bone marrow transplants)• Stroke or cerebrovascular disease• Substance use disorders (alcohol; opioid; or cocaine)

PFIZER CONFIDENTIAL

Table 4. Covariates

Variable	Role	Operational definition
		
use disorder)
 
 • Tuberculosis • Pregnancy or recent pregnancy (for at least 42 days following end of pregnancy). 
Model specification: dichotomous (yes/no)

Number of outpatient visits in the 180 days prior	Patient Characteristics	
Count unique days with an outpatient visit in the 180 days prior to index
 
 • Dichotomous, yes/no • Continuous statistics including mean, standard deviation (SD), median (Q1-Q3), minimum, and maximum. 
Model specification: number categories (0, 1, 2, 3+)

Number of hospitalizations in the 180 days prior	Patient Characteristics	
Count of unique days with an acute hospital admission (POS = 21 and tos_cd = 'FAC_IP.ACUTE') in the 180 days prior to index
 
 • Dichotomous, yes/no • Continuous statistics including mean, standard deviation (SD), median (Q1-Q3), minimum, and maximum 
Model specification: number categories (0, 1, 2+)

Number of prior COVID-19 tests in the prior 365 days	Patient Characteristics	
Count of unique days with COVID-19 test (PCR or antigen test) ordered in the 365 days prior to index
 
 • Dichotomous, yes/no • Continuous statistics including mean, standard deviation (SD), median (Q1-Q3), minimum, and maximum 
Model specification: number categories (0, 1, 2+)

Flu test in the prior 365 days	Patient Characteristics	
Influenza test ordered in the 365 days prior to index
 
 • Dichotomous, yes/no 
Model specification: dichotomous (yes/no)

Number of prior telehealth visits in the prior 365 days	Patient Characteristics	
Count of unique days with telehealth visit in the 365 days prior to index
 
 • Dichotomous, yes/no

PFIZER CONFIDENTIAL

Table 4. Covariates		
Variable	Role	Operational definition
		
 Continuous statistics including mean, standard deviation (SD), median (Q1-Q3), minimum, and maximum 
Model specification: number categories (0, 1, 2+)

Number of labs ordered in the prior 365 days	Patient Characteristics	
Count of unique days with any lab ordered in the 365 days prior to index
 
 Dichotomous, yes/no Continuous statistics including mean, standard deviation (SD), median (Q1 -Q3), minimum, and maximum 
Model specification: number categories (0, 1, 2+)

Prior COVID-19 infection	Patient Characteristics	
1 ICD-10-CM code (U07.1) in the 1 year baseline in any setting (>3 months prior to reflect exclusion criteria
 
Model specification: dichotomous (yes/no)

Prior influenza infection	Patient Characteristics	
1 ICD-10-CM code for influenza in the 1 year baseline in any setting
 
Model specification: dichotomous (yes/no)

If there are conflicting records on the type of influenza vaccine received on index, influenza vaccine category (Enhanced, Standard, Unknown) will be assigned as follows:

1. ≥ 1 NDC or CPT code for an enhanced flu vaccine.
2. Classified as enhanced.
3. ≥ 1 NDC or CPT code for a standard flu vaccine and no codes for enhanced.
4. Classified as standard.
5. ≥ 1 NDC or CPT code for an unknown type of flu vaccine and no codes for enhanced or standard.
 - a. Classified as unknown.

For the influenza vaccine brand subcategories, patients with conflicting records will be classified as “Multiple”.

